10 STUDY PROCEDURES

10.1 Schedule of study procedures

	Screening	Baseline			Follow-up						
	V1 (1-14day before V2)	V2	V3 (up to 3 days after V2)	V4 (up to 3 days after V2)	V5 (4 weeks ± 2 week after V4)	V6 (up to 3 days after V5)	V7 (36 weeks ± 3 weeks)	V8 (up to 1 week after V7)	V9 (62 weeks ± 3 weeks)	V10 (up to 1 week after V9)	
Informed Consent	Х										
Inclusion/exclusion criteria	Х	х									
Demography, medical history	x										
Concomitant medication	x	х			Х		x		X		
Vital signs	Х	х			Х		X		X		
Physical examination	Х	х			Х		x		х		
Pregnancy test (females with childbearing potential)	x	х			х		×		х		
Botnia clamp		х			x		x		х		
Blood sampling	x		х			х		x		Х	
Dual-energy X-ray absorptiometry (DEXA)		х			x		x		х		
Electrocardiography (ECG)	х										
Meal tolerance test (MTT)			x			Х		x		Х	
¹³ C-Urea breath test	x										
Bypass liner insertion				х							
Bypass liner removal							х				
Food frequency questionnaire (FFQ)		x			Х		х		х		
Biopsies				Х			Х				
Adverse Events			Х	Х	Х		х		х		
Stool sampling			Х			Х		x		Х	
Lactulose/Mannitol Test			Х			Х		x		Х	
Gastroscopy											
Abdomen Sonography		x									
Liver Elastography											

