Additionally, at Visit 3 subjects will be instructed by a qualified person to consume a liquid diet the first week after EndoBarrier[™] placement, puree diet during the second week, and normal diet (1200 – 1500 kcal/day) combined with exercise and behaviour modification for the remainder of the implant duration. Participants will also be instructed to take a proton pump inhibitor (40mg BID omeprazole) starting 3 days before the implant through 2 weeks after explant. Daily multivitamin and iron supplements will be provided and recommended for use during the 52 weeks of the implant duration.

- Meal tolerance test
- Blood sampling
- Stool sampling
- Lactulose/Mannitol Test

Visit 4 (Implantation of EndoBarrier[™])

Patient preparation

- 1. Patients must be fasting for 8 hours prior to the procedure.
- 2. Patients must be started on a Proton Pump Inhibitor (40mg twice a day) three days before the procedure and continue regimen until two weeks after the device is removed.
- **3.** Spasmolytics may be used.

Sedation

4. The procedure will be performed under conscious sedation.

Procedural Step

5. Insertion will be performed according to manufacturer instructions

Visit 5 (week 4 ± 2 week)

Study visit 5 will take place not later than six weeks after the implantation of the EndoBarrier[™].

- Physical examination
- Vital signs: resting pulse and blood pressure
- Body weight
- Concomitant medication review
- Botnia clamp
- DEXA
- Adverse events assessment

• Pregnancy Test

Visit 6 (up to 3 days after V5)

Study visit 6 will take place not later than 3 days after V5.

- Meal tolerance test
- Stool sampling
- Blood sampling
- Lactulose/Mannitol Test

Visit 7 (36 weeks ± 3 weeks)

Study visit 5 will take place not later than 39 weeks after the implantation of the EndoBarrier[™]. At this

visit the sleeve will be removed.

- Vital signs: resting pulse and blood pressure
- Body weight
- Concomitant medication review
- DEXA
- Adverse events assessment
- Biospies
- Botnia clamp

Visit 8 (up to 1 week after V7)

Study visit 8 will take place not later than 1 week after V7.

- Vital signs: resting pulse and blood pressure
- Body weight
- Concomitant medication review
- Adverse events assessment
- Meal tolerance test
- Stool sampling
- Blood sampling
- Lactulose/Mannitol Test

Visit 9 (62 weeks ± 3 weeks)

Study visit 9 will take place not later than 29 weeks after the removal of the EndoBarrier[™].

• Physical examination

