- Vital signs: resting pulse and blood pressure
- Body weight
- Concomitant medication review
- Botnia clamp
- DEXA
- Adverse events assessment
- Pregnancy Test

Visit 10 (up to 1 week after V9)

Study visit 8 will take place not later than 1 week after V9.

- Meal tolerance test
- Stool sampling
- Blood sampling
- Lactulose/Mannitol Test
- Study end

Safety visits (after 12, 24 and 48 weeks)

12, 24 and 48 weeks after implantation safety visits will be carried out. As part of these visits blood samples (8ml) will be taken for safety measurements (including blood cell count, iron status, liver function). Additionally, the body weight will be recorded.

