10.3 Laboratory results

All laboratory results will be reviewed and the reports signed by the study physician who will record whether it is normal, abnormal but not clinically significant, or abnormal and clinically significant. In the latter case, the eligibility of the subject will be reviewed.

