12.4. Procedural precautions

A thorough gastroscopic examination of the stomach, pylorus and duodenum should be performed prior to device placement to ensure that the patient's alimentary canal is free of abnormalities which could interfere with the delivery, function and removal of the gastrointestinal liner. This should include observation of the papilla and other accessory ducts. This examination should be made to ensure that they are not located in the bulbous duodenum.

Placement and removal of the EndoBarrier[™] requires the use of fluoroscopic guidance. Only water soluble contrast should be used. Gastrografin or equivalent is recommended. Do not use Barium. Caution should be used to protect the patient's reproductive organs from the effects of radiation.

An incorrectly positioned EndoBarrier[™] may interfere with the bile duct or pylorus. Physicians should remove the incorrectly positioned device in these patients. Do not attempt to drag or push the device into position. Additionally, the EndoBarrier[™] liner should be removed in any patient with clinical and/or chemical evidence of a biliary tract obstruction. Do not leave a device in place with a crossed tip. Crossed tips should be uncrossed by lifting them with endoscopic forceps.

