13 ASSESSMENT OF SAFETY

Safety endpoints: All adverse events reported by the patients will be assessed and reported as outlaid below.

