The Intensity/Severity of the AE should be judged based on the following:

Mild: Awareness of sign(s) or symptom(s) which is/are easily tolerated

Moderate: Enough discomfort to cause interference with usual activity

Severe: Incapacitating or causing inability to work or to perform usual activities

Causal relationship of adverse event

[figure not shown]
Medical judgement should be used to determine the relationship, considering all relevant factors, including pattern of reaction, temporal relationship, dechallenge or rechallenge, confounding factors such as concomitant medication, concomitant diseases and relevant history. Assessment of causal relationship should be recorded in case report forms.

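### No adverse-event enquiry is scheduled between week 4 and liner removal at week 36, although two safety visits fall in that interval

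*Protocol*

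**What the plan says.** **Safety visits.** Protocol section 10.2 places these at weeks 12, 24 and 48 after implantation. It describes their content as "As part of these visits blood samples (8ml) will be taken for safety measurements (including blood cell count, iron status, liver function", and adds a body weight. Nothing else is listed. The section 10.1 table has no column for them.

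**Where AE assessment is itemised.** The visit text in 10.2 lists it at V5, V7, V8 and V9. The AE row of the 10.1 table is marked at V3, V4 (liner insertion), V5, V7 and V9.

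**Timing.** The table gives "V5 (4 weeks ± 2 week after V4", V4 being the implantation. For the next visit, "Study visit 6 will take place not later than 3 days after V5"; neither text nor table gives it an AE item. V7 is at week 36 ± 3 and is the removal visit. V8 follows within a week, and V9 is at week 62 ± 3.

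**Collection and recording.** Section 13 opens with "All adverse events reported by the patients will be assessed and reported as outlaid below". Its reporting procedure then requires every AE, whether serious or not, to be documented from consent until 28 days after the trial, with start date, end date and severity. The lowest grade is "Mild: Awareness of sign(s) or symptom(s) which is/are easily tolerated".

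**Laboratory results.** Under section 10.3 the study physician grades each result. If it is abnormal and clinically significant, "In the latter case, the eligibility of the subject will be reviewed". Section 12.4 separately says that the "liner should be removed in any patient with clinical and/or chemical evidence of a biliary tract obstruction".

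**The concern.** The visits named as safety visits omit the basic safety question, and two of them fall in the longest interval between scheduled enquiries while the liner is in place. Elsewhere section 10.2 writes AE assessment out as a visit item, so a site working from the lists has no prompt to ask at weeks 12 and 24.

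Section 8 says that the pilot should give insight into the safety of the device. An event soon after V5 that the patient does not mention unprompted would first be asked about at V7, about 32 weeks later. By then its start date, end date and severity rest on long recall. Easily tolerated complaints on the protocol's own list of potential AEs, such as bloating, flatulence or cramping, are the most likely to be forgotten or misdated. The expected direction is a lower count of mild and transient events.

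**Working it through.** The plan states no figure to reproduce. The check sets the visit lists beside the table and measures the gaps between scheduled AE enquiries, in weeks from implantation.

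**1. Scheduled enquiries, implantation to removal.** V4 at week 0 (table only), V5 at week 4 (text and table) and V7 at week 36 (text and table). V6 and the week 12 and 24 visits list none.

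**2. Present gap with the device in place.**
- Nominal: 36 − 4 = 32 weeks.
- V5 can fall in weeks 2 to 6 and V7 in weeks 33 to 39.
- Shortest: 33 − 6 = 27 weeks. Longest: 39 − 2 = 37 weeks.
- Nominal share of planned device time: 32/36 = 89%. This time lies between two enquiries; it is not unobserved time.

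**3. Gap with AE assessment added at weeks 12 and 24.** The protocol gives these visits no window, so they are assumed to be held on the stated weeks.
- V5 to week 12: 12 − 4 = 8 weeks (6 to 10 with the V5 window).
- Week 12 to week 24: 12 weeks.
- Week 24 to V7: 36 − 24 = 12 weeks (9 to 15 with the V7 window).
- The longest gap is 12 weeks nominal, and up to 15 with windows.

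**4. After removal.** V8 is taken at its latest nominal time, week 37.
- At present, V8 to V9: 62 − 37 = 25 weeks.
- With week 48 added: 48 − 37 = 11 and 62 − 48 = 14 weeks. The longest is 14, or 65 − 48 = 17 if V9 falls at week 65.
- If the table is followed and V8 carries no AE assessment, the present gap is V7 to V9: 62 − 36 = 26 weeks.

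**5. Added work.** The protocol's 12 subjects × 3 visits = 36 enquiries at most, of which 12 × 2 = 24 are while the device is in place. With the SAP's 10 subjects the total is 10 × 3 = 30.

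**6. What cannot be calculated.** The documents give no event rates and no rate at which patients volunteer symptoms, so the number of events missed or misdated cannot be derived.

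**The case against.** The strongest reply is that collection is already required. The reporting procedure in section 13 covers all AEs continuously from consent, and the V7 enquiry can look back over the whole interval. This stands. A reader might infer from the schedule that AEs between weeks 4 and 36 go uncollected; the documents do not support that. An AE that a patient mentions, or that staff notice, at week 12 or 24 must be recorded.

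A second reply is that the visit lists are not exhaustive, since text and table disagree in several places. V8 has AE assessment in the text only and V4 in the table only, and the V7 text omits the physical examination that the table marks. Staff may well ask about AEs at a visit called a safety visit. This also stands in part: omission from a list does not prove that nobody will ask. But where AE assessment is written out at other visits, leaving it off these ones is a gap in the plan worth closing.

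Three further inferences go too far.
- A reader might say that enquiry with the device in place is confined to weeks 4 and 36. The table also marks AEs at V4.
- A reader might count week 48 as device time. Removal is planned at V7, so week 48 bears only on follow-up after removal. The mention in 10.2 of a 52-week implant duration, in connection with supplements, conflicts with this, but the V7 text on removal is explicit.
- A reader might take the section 13 reference to patients' reports as excluding events that clinicians detect, or section 10.3 as leaving abnormal results without action. The AE definition in 13.1 is general, the reporting procedure covers all AEs, and 12.4 already directs removal for biliary obstruction. What 10.3 lacks is a cross-reference.

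The SAP's lack of a named AE summary is a separate matter, and this point does not rest on it.

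**Conclusion.** The point holds in a limited form. As written, the plan schedules no AE enquiry for 32 weeks (27 to 37 with windows) of a 36-week implant, and two visits already planned inside that gap could carry one.

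The consequence is confined mainly to mild or transient events that patients do not volunteer. These may be under-counted, or recorded with poor dates. Serious events are much less exposed, because they usually come to attention without a scheduled question. Efficacy results are little affected, and nothing here touches the error rate or power.

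The conclusion assumes removal at V7 as the visit text states, safety visits held on their nominal weeks, and visit lists followed as written. If sites ask about AEs at the safety visits anyway, the practical loss is smaller still. This is a cheap improvement of minor severity.

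**What to change.** - Add an AE assessment to the week 12 and week 24 safety visits in section 10.2, and to the week 48 visit for follow-up after removal.
- Give these three visits columns in the section 10.1 table.
- Optionally, add a sentence to section 10.3: after implantation, a clinically significant laboratory result is assessed as a possible AE and against the section 12.4 removal criterion, not only for eligibility.

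The cost is at most 36 brief enquiries at visits that already take place, a few more form entries and small text edits. The reported count of mild AEs may rise. No new procedure is needed.

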7.2 Secondary outcome measures

- Plasma concentrations of incretins (GLP-1 and GIP) and its time profiles during MTT
- OGTT calculations and modelling describing beta cell response to oral glucose load; insulin and c-peptide areas under the curve during OGTT

- Change in gut permeability (Lactulose/Mannitol Test)

Medizinische Universität Graz

- Weight loss will be reported as percentage of excess body weight loss (%EBWL) 4 and 36 weeks after EndoBarrier[™] implantation as well as 6 months after removal of the EndoBarrier[™]
- Changes in cardiovascular risks (non-fatal and fatal coronary heart disease, fatal coronary disease, non-fatal and fatal stroke as well as fatal stroke)
- Changes in gut microbiota

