- 2) To assess changes in body weight from baseline to 4 weeks, 36 weeks and 62 weeks, respectively.
- 3) To determine changes in gut permeability and gut microbiome composition from baseline to 4 weeks, 36 weeks and 62 weeks, respectively.
- 4) To evaluate changes in area under curve (AUC) of glucose from baseline to 4 weeks, 36 weeks and 62 weeks, respectively.
- 5) To assess changes in body composition assessed by Dual-energy X-ray absorptiometry (DEXA) from baseline to 4 weeks, 36 weeks and 62 weeks, respectively.
- 6) To evaluate correlations between mixed meal tolerance test (MMTT) and Botnia clamp results regarding insulin sensitivity and beta-cell function.
- 7) To determine changes in cardiovascular risk as assessed by the United Kingdom Prospective Diabetes Study (UKPDS) risk engine from baseline to 4 weeks, 36 weeks and 62 weeks, respectively.

Study Methods

Inclusion and Exclusion Criteria

Inclusion criteria

- Participant is willing and able to give informed consent for participation in the study.
- Male or female
- Age: 18 70 years
- Type 2 diabetes
- BMI 30-49 kg/m²
- HbA1c \geq 6.5% (48 mmol/mol)
- Appropriate lifestyle intervention measures have been tried but have failed to achieve or maintain adequate, clinically beneficial weight loss for at least 6 months
- Person is generally fit for intervention
- Person commits to the need for long-term follow-up

Exclusion criteria

- Type 1 diabetes mellitus
- Maturity Onset Diabetes of the Young (MODY)
- Secondary diabetes due to a specific disease or glucocorticoid therapy
- Pregnancy or women of childbearing age without adequate contraception
- Women who are breast-feeding
- Hypothalamic cause of obesity, Cushing syndrome
- Major psychiatric disease including diagnosed eating disorders, history of drug or alcohol abuse
- History of bariatric surgery or complex abdominal surgery
- Inflammatory bowel disease
- Pancreatitis
- Cholelithiasis
- Uncontrolled gastroesophageal reflux
- Known upper GI bleeding conditions, e.g. gastric or esophageal varices
- Congenital or acquired abnormalities of the upper GI tract, e.g. stenosis
- Subjects with or a history of coagulopathy, upper gastro-intestinal bleeding conditions such as esophageal or gastric varices, congenital or acquired intestinal telangiectasia
- Chronic non-steroidal anti-inflammatory drug (NSAID) or aspirin treatment (Subjects unable to discontinue NSAIDs (non-steroidal anti-inflammatory drugs) during the implant period)

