- Previous GI surgery that could affect the ability to place the device or the function of the implant
- GLP-1 receptor agonist therapy

- Known ischaemic heart disease or heart failure
- History of stroke
- Active Helicobacter pylori (Note: Subjects may be enrolled if they had a prior history of Helicobacter Pylori and were successfully treated)
- Actual iron deficiency anemia
- Subjects or Family history of a known diagnosis or pre-existing symptoms of systemic lupus erythematosus, scleroderma, or other autoimmune connective tissue disorder
- Known malignancy or any other multimorbid patient condition or circumstance, which, in the opinion of the investigator, would affect the patient's ability to participate in the protocol or would put the participant at an unjustified risk

Clinical endpoints

Primary endpoints

- Change in the glucose infusion rate (Botnia Clamp) adjusted for body weight at baseline from baseline to 4 and 36 weeks after the Endobarrier implantation, respectively
- Change in early insulin response from baseline to 4 and 36 weeks after the Endobarrier implantation, respectively

Secondary endpoints

- Change in the glucose infusion rate (Botnia Clamp) adjusted for body weight at baseline from baseline to 24 weeks after the Endobarrier explantation
- Change in early insulin response from baseline to 24 weeks after the Endobarrier explantation, respectively
- Change in body mass index from baseline to 4 and 36 weeks after the Endobarrier implantation and 24 weeks after the Endobarrier explantation
- Change in body weight from baseline to 4 and 36 weeks after the Endobarrier implantation and 24 weeks after the Endobarrier explantation
- Change in HbA1c from baseline to 4 and 36 weeks after the Endobarrier implantation and 24 weeks after the Endobarrier explantation
- Change in lactulose/mannitol ratio from baseline to 4 and 36 weeks after the Endobarrier implantation and 24 weeks after the Endobarrier explantation
- Change in glucose AUC (MMT) from baseline to 4 and 36 weeks after the Endobarrier implantation and 24 weeks after the Endobarrier explantation
- Change in c-peptide AUC (MMT) from baseline to 4 and 36 weeks after the Endobarrier implantation and 24 weeks after the Endobarrier explantation
- Change in UKPDS CHD risk from baseline to 4 and 36 weeks after the Endobarrier implantation and 24 weeks after the Endobarrier explantation

Sample Size

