Insulin sensitivity will be assessed as the mean/median glucose uptake, calculated from the glucose infusion rates during the last 60 minutes of the euglycemic clamp (GIR), which will be adjusted for baseline body weight. Changes in body weight will be analyzed as the difference in absolute total body weight, change in BMI, excess weight loss, and total body weight loss. Changes in T2DM will be analyzed as the absolute change in HbA1c, fasting plasma glucose, and changes in T2DM medication. Differences in lipid levels and blood pressure will be analyzed as absolute differences.

The repeated measures analysis of variance (ANOVA) or Friedman test will be applied to compare parameters over time and the Durbin–Conover test with Bonferroni corrections will be applied for post hoc multiple pairwise comparisons of parameters.

The weight adjusted glucose infusion rate (GIR) changes will be assessed with a multilevel non-linear mixed model with post hoc multiple comparison and Bonferroni corrections. All statistical analyses will be conducted in Stata version 17.0 and R version 4.0.

Missing data

Missing data will be treated as such, and no data will be imputed.

Level of significance

The two-sided alpha level of <0.05 will considered to decide statistical significance.

Data presentation

Baseline characteristics will be tabulated for all patients. The results of primary and secondary outcomes will be presented both in tables and bar graphs, as appropriate.

References

1. Coutinho W L, T. World Obesity Day Press Release. World Obesity Federation 2015.

4. Intensive blood-glucose control with sulphonylureas or insulin compared with conventional treatment and risk of complications in patients with type 2 diabetes (UKPDS 33). UK Prospective Diabetes Study (UKPDS) Group. *Lancet* 1998; **352**:837-853.

5. Tight blood pressure control and risk of macrovascular and microvascular complications in type 2 diabetes: UKPDS 38. UK Prospective Diabetes Study Group. *Bmj* 1998; **317**:703-713.

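### Body weights taken at weeks 12, 24 and 48 have no role in the SAP's weight analysis; the loss at week 36 is modest and arises only if some week-36 weights are missing

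*Protocol*

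**What the plan says.** **Collection.** Protocol 10.2 ends with this schedule: "12, 24 and 48 weeks after implantation safety visits will be carried out". After listing safety blood tests it adds "Additionally, the body weight will be recorded". The other post-baseline weights listed there are at V5 (week 4), V7 (week 36), V8 (up to one week after V7) and V9 (week 62). Counting the safety visits, seven post-baseline weights are scheduled.

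**Device status.** At V7 (36 ± 3 weeks), "visit the sleeve will be removed". Weeks 12 and 24 then fall before removal and week 48 after it. The V3 text in the same section, however, gives supplements as "recommended for use during the 52 weeks of the implant duration". These statements conflict and must be reconciled.

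**Use.** Protocol 7.2 has "Weight loss will be reported as percentage of excess body weight loss (%EBWL) 4 and 36 weeks after EndoBarrier", plus six months after removal. The SAP's secondary objective reads "To assess changes in body weight from baseline to 4 weeks, 36 weeks and 62 weeks, respectively". Its secondary endpoint reads "Change in body weight from baseline to 4 and 36 weeks after the Endobarrier implantation and 24 weeks after the Endobarrier explantation", and BMI has the same times. Weeks 12, 24 and 48 appear in no weight objective, outcome or endpoint.

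**Method.** Under Statistical procedures, the SAP compares parameters over time by repeated-measures ANOVA or Friedman test and names a mixed model for the glucose infusion rate only. Under Missing data: "Missing data will be treated as such, and no data will be imputed".

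**The concern.** With windows of 4 ± 2 weeks for V5 and 36 ± 3 weeks for V7, the gap between them is 27 weeks (33 − 6) to 37 weeks (39 − 2). Protocol 9.4 foresees withdrawal for adverse events, non-compliance and loss to follow-up, and this gap is where much of it could fall. The week-12 and week-24 weights are the only scheduled ones inside it.

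A subject who leaves after week 24 has weights that say something about week 36, but a complete-block analysis of baseline, week 4, week 36 and the post-explant visit cannot use them. At stake is the precision of the mean 36-week change in weight and BMI. If subjects with poor weight loss leave more often, bias in that mean is at stake too.

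**Working it through.** The plan states no power, SD, dropout rate or precision for weight, so there is no figure to reproduce. From the documents: N = 12 (Protocol 8) or 10 (SAP, Sample Size), and the visit times above. Everything else below is assumed.

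**1. How likely is a gap at week 36?** The chance that at least one subject is missing is 1 − (1 − p)^N. For p = 5%, 10% and 20% it is 40%, 65% and 89% (N = 10), or 46%, 72% and 93% (N = 12).

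**2. What does a gap cost in all?** The 95% CI half-width of a mean change in SD units is t(0.975, n − 1)/√n: 0.635 (n = 12), 0.715 (n = 10), 0.836 (n = 8). Two missing subjects widen it by 0.715/0.635 − 1 = 13% from 12, or 0.836/0.715 − 1 = 17% from 10.

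**3. How much does week 24 recover if subjects are missing by chance?** Let m be the number missing at week 36 with week 24 observed, n₁ = N − m, and r the correlation between the week-24 and week-36 changes. In units of the week-36 variance:

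- complete cases: 1/n₁
- likelihood estimate using week 24: (1 − r²)/n₁ × [1 + (m/N)/(n₁ − 3)] + r²/N

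Example, N = 10, m = 1, r = 0.7: 0.51/9 × (1 + 0.1/6) + 0.49/10 = 0.1066, against 1/9 = 0.1111. The SE ratio is √(0.1066/0.1111) = 0.98, a 2% cut.

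Example, N = 10, m = 3, r = 0.9: 0.19/7 × (1 + 0.3/4) + 0.81/10 = 0.1102, against 1/7 = 0.1429. The ratio is 0.878, a 12% cut.

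Cut in SE (%). The last column is the ceiling, 1 − √(n₁/N), reached only if nothing were missing:

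| N, m | r = 0.3 | r = 0.7 | r = 0.8 | r = 0.9 | r = 0.95 | ceiling |
|---|---|---|---|---|---|---|
| 10, 1 | −0.3 | 2.0 | 2.9 | 4.0 | 4.5 | 5.1 |
| 10, 2 | −0.9 | 4.0 | 5.9 | 8.0 | 9.3 | 10.6 |
| 10, 3 | −2.0 | 5.6 | 8.6 | 12.2 | 14.2 | 16.3 |
| 12, 1 | −0.1 | 1.8 | 2.5 | 3.3 | 3.8 | 4.3 |
| 12, 2 | −0.3 | 3.5 | 5.0 | 6.8 | 7.7 | 8.7 |
| 12, 3 | −0.8 | 5.2 | 7.5 | 10.3 | 11.8 | 13.4 |

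At r = 0.3 there is no gain. For N = 10, m = 2 and r = 0.8 to 0.95, the effective sample size (1/variance) rises from 8 to between 9.0 and 9.7.

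**4. Bias, simple bound.** If those missing lost a fraction f as much weight as the others, the complete-case mean overstates the loss by N/[(N − m) + m·f] − 1. For (N, m) = (10, 2), (12, 2), (12, 3) and f = 0.3 to 0.5 this is 9 to 21%. The low end is 12/11 − 1 = 9%; the high end is 12/9.9 − 1 = 21%.

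**5. Bias, simulated.** There were 6,000 runs per setting. Assumed SDs of change were 2.5, 4.5, 6 and 7 kg at weeks 4, 12, 24 and 36, with correlation 0.7 or 0.9 per 12 weeks. Poor week-24 loss drove missingness, so that 11 to 26% were missing at week 36.

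| Estimate of the 36-week mean | Overstatement of loss |
|---|---|
| complete cases | 0.65–1.76 kg (0.09–0.25 of the 7 kg SD) |
| regression on week 4 only | 0.24–1.10 kg |
| regression on week 24 | at most about 0.05 kg |

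Here the gain is in bias, not in spread. At N = 10, r = 0.7 and 25% missing, the SD of the estimate was 2.45 kg for complete cases and 2.70 kg using week 24. Root mean square error was √(1.44² + 2.45²) = 2.84 kg against 2.70 kg. At r = 0.9 it was 2.95 kg against 2.36 kg.

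**6. More visits under the same method would not help.** At 5% missing per visit, complete cases fall from 0.95³ = 85.7% with three post-baseline visits to 0.95⁶ = 73.5% with six.

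**The case against.** The protocol calls these safety visits and pairs the weight with blood count, iron status and liver function. Recording a safety measure without making it an efficacy time point is ordinary design. Weight is secondary, the trial is a pilot without a power calculation, and the primary endpoints are not measured at these visits. All of that stands and limits the weight of the point. But neither document says that these weights are for safety only.

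A reader might go further than the documents allow:

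- *The weights are certainly discarded.* The SAP does not state listwise deletion. Friedman needs complete blocks, but some repeated-measures ANOVA software keeps a subject's other rows. Hence a subject may, not must, drop out.
- *The unused visits cause the whole loss.* Part of the gain comes from moving to a likelihood method. Week 4, already an SAP visit, takes the simulated bias from 0.65–1.76 kg to 0.24–1.10 kg by itself.
- *Nothing else is near week 36.* V8 lists body weight within a week of V7, so a subject who misses only V7 may have a usable value. The SAP has no rule for using it, and it does not help early leavers.
- *Week 48 alone shows regain.* Week 62 against week 36 shows it too; week 48 adds an intermediate point. Under the 52-week wording it would not be a post-removal weight.
- *The data are already in the case report form.* The form is not among the documents, and the schedule table in Protocol 10.1 has no safety-visit columns.

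The remedy can also be done badly. A linear random slope over 62 weeks does not suit a course that may fall and then rise, and plain AR(1) does not suit gaps of 4, 8, 12, 12, 12 and 14 weeks. If a subject loses the device after week 24, a model that predicts week 36 from on-device weights answers as if the device had stayed, and this can itself overstate the loss.

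**Conclusion.** The omission is a matter of record: three scheduled post-baseline weights have no stated analytic use, and the planned method may drop a subject who has them. The consequence is modest. With 1 to 3 subjects missing by chance, using week 24 cuts the SE of the mean 36-week change by about 2 to 12% for r of 0.7 to 0.9, and by up to 14% at N = 10, three missing and r = 0.95. There is no gain at r of about 0.3, and none if nobody is missing.

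The documents do not support saying that the 36-week result is biased. Overstatement arises only if missingness relates to the weight course; the 9 to 21% and the 0.65 to 1.76 kg hold only under the assumptions above. The dropout rate, correlation, SDs and leaver effect are all assumed. This is a worthwhile refinement to a secondary endpoint, not a flaw in the primary analysis.

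**What to change.** In the SAP, for body weight and for BMI, replace the ANOVA/Friedman comparison with one likelihood-based linear mixed model on all scheduled weights (weeks 0, 4, 12, 24, 36, 48, 62):

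- visit as a categorical effect;
- a random subject intercept with continuous-time (spatial-power) residual correlation, which suits the unequal gaps;
- Kenward-Roger degrees of freedom;
- the V8 weight as the week-36 value if V7 is missing;
- changes from baseline at weeks 4, 36 and 62, each with a 95% CI;
- a statement of how weights after early device loss are handled, and so of what the week-36 mean estimates.

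Report week 48 descriptively, or as an intermediate post-removal point once removal at V7 and the 52-week implant wording are reconciled. If the team prefers to leave these weights out, one SAP sentence should say that they serve safety monitoring only.

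The cost is SAP wording and a little code, with no new measurements. The downside is an assumed covariance structure, because an unstructured one is not workable with 10 to 12 subjects and seven visits. Show the observed-case result alongside as a check.
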